**SECTION B: FUNDING**

Provide information regarding **ALL** funding sources for this project, including existing funding, pending funding, and funding that has been applied for to support this research.

Please check all that apply:	
	This research is funded
	Funding has been requested Have you received Just In Time (JIT) Notification?  Yes  No NOTE: Once the funding has been awarded, submit an amendment to the IRB to add the funding source
	Research is not funded

**If the research is funded or funding has been requested, it is REQUIRED that you complete the box below.** If you don't have an award #, please state that in the box below. If you have multiple funding sources, add additional boxes as necessary.

Sponsor Name	Boston University Neuromotor Recovery Laboratory
Title of Grant/Proposal	A soft, hybrid robotic exosuit neuroprosthesis (reNeu) for post-stroke gait assistance and rehabilitation
Sponsor Award # (REQUIRED)* *If Award is pending, put "pending".	Not applicable

YES	NO	
		Is Boston University the Prime Awardee of the grant?
		Is Boston University receiving a sub-award? Name of Prime Recipient:
		Is the research being supported by an Industry Contract or Clinical Trial Agreement?

**\*NOTES:**

- Provide a copy of the grant application, funding proposal, contract/agreement, scope of work, or sub-award agreement supporting the research. If an award is pending, once the funding has been awarded, submit an amendment to the IRB to add the funding source.
- If this research study is for your dissertation, provide a copy of your prospectus (if available).

## **SECTION C: CONFLICT OF INTEREST**

 YES (REQUIRED)	
I confirm that ALL those responsible for the design, conduct, or reporting of the proposed research, including at minimum, all Senior/key personnel in the grant application, have completed the financial interest disclosure forms, submitted them to the COI office, and completed training as dictated at: http://www.bu.edu/researchsupport/compliance/conflicts-of-interest/, and as provided under the Boston University Investigator Conflicts of Interest Policy for Research.
 
NOTE: You must attach a copy of the PI's COI submission confirmation email. COI submission confirmation emails for all other study staff should be maintained at the research site.

Of the financial interest disclosure forms submitted, did you check “yes” to any of the questions on either the FIND1 or NONFIND1 form?       Yes*     No
	

**\*If you checked “yes” to any of the questions on either the FIND1 or NONFIND1 form, the IRB Director will contact the COI office to obtain the disclosure information.**

## **SECTION D: TYPE OF REVIEW**

For Guidance regarding Type of Review please refer to the [CRC IRB website](#)

I. **FULL BOARD**

Please refer to the [CRC IRB website](#) for Full Board submission deadlines and meeting dates.

II. **EXPEDITED**

In order to qualify for expedited review, the study must be no more than minimal risk\* **AND** must fall into one of the categories below. Check all that apply:

- Clinical studies of drugs and medical devices only when an investigational new drug application (IND) or investigational device exemption application (IDE) is not required

2.  Collection of blood samples by finger stick, heel-stick, ear stick, or venipuncture as follows:
  - a. From healthy, nonpregnant adults who weigh at least 110 pounds. For these subjects, the amounts drawn may not exceed 550 ml in an 8-week period and collection may not occur more frequently than 2 times per week; or
  - b. From other adults and children, considering the age, weight, and health of the subjects, the collection procedure, the amount of blood to be collected, and the frequency with which it will be collected. For these subjects, the amount drawn may not exceed the lesser of 50 ml or 3 ml per kg in an 8-week period and collection may not occur more frequently than 2 times per week.
3.  Prospective collection of biological specimens for research purposes by noninvasive means. Examples include hair and nail clippings, saliva or cheek swabs, sweat, etc.
4.  Collection of data through noninvasive procedures (not involving general anesthesia or sedation) routinely employed in clinical practice, excluding procedures involving x-rays or microwaves. Where medical devices are employed, they must be cleared/approved for marketing. Examples:
  - Physical sensors that are applied either to the surface of the body or at a distance and do not involve input of significant amounts of energy into the subject or an invasion of the subject's privacy
  - Weighing or testing sensory acuity
  - Magnetic resonance imaging
  - Electrocardiography, electroencephalography, thermography, detection of naturally occurring radioactivity, electroretinography, ultrasound, diagnostic infrared imaging, doppler blood flow, and echocardiography
  - Moderate exercise, muscular strength testing, body composition assessment, and flexibility testing where appropriate given the age, weight, and health of the individual
5.  Research involving materials (data, documents, records, or specimens) that have been collected, or will be collected solely for non-research purposes (such as medical treatment or diagnosis)
6.  Collection of data from voice, video, digital, or image recordings made for research purposes.
7.  Research on individual or group characteristics or behavior (including research on perception, cognition, motivation, identity, language, communication, cultural beliefs or practices, and social behavior) or research employing survey, interview, oral history, focus group, program evaluation, human factors evaluation, or quality assurance methodologies.

**Note: The IRB will make the final determination on the Type of Review**

**\*Minimal risk** means that the probability and magnitude of harm or discomfort anticipated in the research are not greater in and of themselves than those ordinarily encountered in daily life or during the performance of routine physical or psychological examinations or tests.

## **SECTION E: STUDY STAFF AND HUMAN SUBJECTS TRAINING**

List **ALL** current members of the research team in the table below. Add more rows as necessary.

### **STUDENT RESEARCH:**

The Faculty Advisor must be listed as a co-investigator in this section and must complete the Human Subjects training requirements. Faculty Advisors are responsible for reviewing the IRB application, agreeing to serve as the Co-PI for this study with the student and are responsible for the ethical conduct of this student's human subjects research. Faculty Advisors must sign this Application prior to it being submitted to the IRB.

## **REQUIRED GOOD CLINICAL PRACTICE TRAINING FOR NIH-FUNDED CLINICAL TRIALS**

		NIH-FUNDED CLINICAL TRIALS
YES*	NO	
		Is your study NIH-Funded AND meet the definition of a clinical trial as defined in the NIH policy ?

		
Is the BU PI the lead investigator OR is BU the lead site for this research?
 
Note: This box only needs to be completed if the off-site location is engaged in the research.
 
*If YES, provide the following information in this box:
 

• The plan for collection and management of data from all the sites

○ Data collected at Boston University, Harvard University, and Spaulding Rehabilitation Hospital will be encrypted and password-protected and stored on either a private network drive, SharePoint folder, or REDCap. The private network drive will be used for backup storage. Identifiable information, project documents, and de-identified biomechanical and photo/video data will be stored on the SharePoint folder, which is accessible only by the research team. Clinical documents and surveys will be scanned and uploaded to REDCap. Any documents that are handwritten will be scanned and transported back to BU or shredded once electronically uploaded.

• The plan for reporting and evaluating:

○ Unanticipated problems

○ Serious and/or continuing non-compliance

○ Suspensions and terminations of research

○ Interim results

○ Protocol modifications

*** All reporting will be directed to both the individual site PIs and the overall project PI, either at a biweekly team meeting or immediately if the problem or non-compliance is serious or urgent.

***

• The name of the Principal Investigator from each site

○ Boston University: [name]

○ Harvard University: [name]

○ Spaulding Rehabilitation Hospitals: [name]

YES*	NO	
		Will this research be conducted outside of the United States? If YES, complete the International Research Form .

## **SECTION G: STUDY SUMMARY**

**Summarize the study in lay language (do not copy from the grant/scope of work/proposal, etc.). This summary should include the research design, purpose, objectives, research question, hypothesis, and any relevant background information.**

Do not include a list of citations in this section. Please limit this section to no more than 300 words.

Stroke is the leading cause of disability worldwide, resulting in nearly \$35B annual costs to the US alone. The restoration of walking is a primary goal of post-stroke recovery, yet existing rehabilitation approaches and assistive technologies fail to sufficiently ameliorate post-stroke gait deficits, resulting in poor long-term outcomes. Muscles are biological motors that have been optimized for bipedal locomotion. Despite their weakened state, the muscles of people post-stroke retain a remarkable capacity to produce large magnitudes of force that patients are unable to voluntarily access during functional activities. Our team of engineers, clinicians, and scientists are working to develop a textile-based neuroprosthesis, the reNeu, that uses a clothing-like human-device interface to harness the power of electricity to bypass the damaged neural circuitry and exploit the residual force generating capacity of post-stroke muscle. In addition to having an immediate effect when worn, our past research has shown that long-term use of a neuroprosthesis during gait training can lead to durable gait restoration that is not dependent on continued use of the stimulation.

The aims of this project are two-fold: 1) to create a device that uses electrical stimulation to improve walking after stroke; and 2) to integrate the electrical stimulation device in Aim 1 with a previously developed soft robotic exosuit to optimize the restorative potential of wearable rehabilitation devices.

The electrical stimulation device being developed in Aim 1 (referred to as reNeu) delivers small bursts of electrical current to enable muscles to perform body movements, a technique called functional electrical stimulation (FES). The reNeu will use wearable sensors to detect an individual's unique gait pattern. These sensors, integrated with flexible apparel, will enable electrical stimulation to be delivered adaptively to the muscles of the affected lower limb based on an individual's specific gait pattern. Initial developments of the reNeu will focus on assistance of the ankle, whereas further developments will progress to assistance of the knee, hip, or a combination of lower limb joints.

We believe that both the level and timing of stimulation assistance will affect walking quality and hypothesize that individualized adaptive assistance will improve walking quality compared to fixed assistance (i.e. same level and timing for all individuals). More specifically, we hypothesize that changes in plantarflexor FES will alter the forward propulsion and walking speed of individuals post-stroke. To test the hypotheses, participants will walk with several different stimulation profiles, i.e. combinations of stimulation level (low-high) and timing (early-late). Initial development studies will be performed on the treadmill to determine specific biomechanical mechanisms being altered by the reNeu and will inform further adjustments of stimulation profiles to best assist the user. Testing will progress from treadmill to overground to assess feasibility of using the reNeu in a community setting, and training studies using the reNeu will identify potential therapeutic benefits of the device.

For Aim 2 of the study, the aforementioned stimulation device will be integrated into a soft robotic exosuit previously designed by members of the lab and its affiliates. This new FES-integrated exosuit will combine neuromuscular assistance from FES with mechanical assistance provided by the exosuit. We hypothesize that FES-integrated exosuits will improve walking quality better than either device alone, by improving walking speed and distance while reducing overall energy expenditure. We also hypothesize this hybrid device will reduce device energy costs (e.g. motor power, electrical current) compared to either device alone, by modulating between FES (neuromuscular) and exosuit (mechanical) assistance in response to muscle fatigue and required energy for a particular functional task. These hypotheses will be verified by studies comparing walking with the stimulation device (from Aim 1), the exosuit, and the FES-integrated exosuit. Muscle fatigue and system power consumption will be monitored, as well as metabolic expenditure and biomechanical measures.

Activities performed in this study will be categorized into one of three research phases. Phase 1 consists of Device Development visits which include walking with and without the FES device. These visits are standalone visits to inform development decisions from the research team. Phase 2 consists of Device Testing visits which include walking with and without the FES device with a combination of assistance profiles. These visits may span multiple sessions to validate device developments. Phase 3 consists of Training Studies which include walking with and without the FES device with the intent of providing rehabilitative effect. These visits will span multiple sessions at a pre-defined frequency to provide standardized training for all participants and evaluate long-term rehabilitative effects of the device. Please see Section L for more detail on research phases.

Individuals enrolled in this study will be categorized into one of two groups. Group 1 participants must be currently undergoing active rehabilitation under the guidance of a therapist/physiatrist. This rehabilitation must be active at the time of secondary screening and independent of procedures conducted in this study. Participants identified as Group 1 will remain in Group 1 for as long as their clinical rehabilitation is active. Group 2 participants are those who are not undergoing active rehabilitation at the time of the secondary screening visit and throughout their participation in the study. If a Group 2 participant begins clinical rehabilitation while participating in the study, that participant will become a Group 1 participant. Both Group 1 and Group 2 participants are eligible to participate in any of the activities in the three research phases. Please see Section I for more detail on participant groups.

## **SECTION H: RESEARCH METHODS AND ACTIVITIES**

**(Check all that apply)**

	Collection of audio, video, digital, or image recordings
	Biological samples → Complete Biological Samples Form Examples: blood, hair, cheek swab, urine, tears, saliva, etc.
	Collection of data that may be sensitive and if disclosed could put subjects at risk for legal or social harms. (e.g. Illegal behaviors, HIV status, psychiatric illness, information related to sexual behaviors, etc.)
	Coordinating Center/Lead Site
	Deception
	Devices → Complete Devices Form
	Drugs → Complete Drugs Form
	Ethnographic: The study of people in their own environment through the use of methods such as participant observation and face-to-face interviewing
	Focus Groups
	Genetics Testing → Complete Genetics Form
	MRI
	Placebo
	Pregnancy Testing
	Randomization
	Surveys, interviews, questionnaires

	Secondary Data Analysis
	Other (please describe): Common clinical examination approaches will be used to measure cognition, sensorimotor function, and walking ability. Additionally, non-invasive measurements of biomechanical function will be made using common movement analysis tools such as an instrumented treadmill, forceplates, optical motion tracking cameras, and motion tracking sensors attached to the body (see section L for more details).

## **SECTION I: PARTICIPANT POPULATION**

**Provide the Number of Participants to be Enrolled. If you have sub-groups or more than one arm, please separate out these enrollment numbers. Note:** Please account for participants who may drop out or be withdrawn from the study. Anyone who signs a consent form is considered to be enrolled in the research regardless of whether they complete any study procedures.

This study has a target enrollment of up to 40 participants who have had a stroke and 40 participants who have not had a stroke. Participants with post-stroke hemiparesis will participate in the patient-in-the-loop development of a novel neuroprosthesis that harnesses the power of electricity to exploit the residual force generating capacity of post-stroke muscles during functional activities. These participants may be enrolled into one of two groups (depending on whether they are in an active rehabilitation program) and may participate in as many of the three phases of this study (listed below) as they wish. Healthy participants will also participate in the patient-in-the-loop development of this novel neuroprosthesis and will be enrolled into a healthy participant group. Healthy participants may partake in device development and testing phases of this study. Regardless of participant group or research phase, the target enrollment for the entire study across all approved research sites will not exceed a total of 80 participants. Participants who complete screening at one research site will complete subsequent testing at the same location, or at the testing site that is most convenient for that participant. Participants may switch study sites if they wish, however all visits for a particular sub-study (e.g. a clinical training study in Phase 3) must be conducted at the same site.

### Participant Groups:

- Group 1: participants post-stroke currently undergoing rehabilitation under the guidance of a therapist/physiatrist (independent of research procedures for this study). Rehabilitation program must be active at the time of the secondary screening visit.
- Group 2: participants post-stroke not currently undergoing rehabilitation under the guidance of a therapist/physiatrist (independent of research procedures for this study).
- Healthy: participants who have not had a stroke

### Research Phases:

- Phase 1: Device Development
- Phase 2: Device Exposure & Testing
- Phase 3: Clinical Training Studies

**Check all categories that apply to your participant population:**

	Adults
	Children (< 18 years of age)
	Adults with Limited Decision-Making Capacity
	Non-English Speaking
	Prisoners
	BU Employees
	BU Students
	Wards of the state
	Other (please describe):

If a population other than 'Adults' has been checked, describe the additional safeguards that have or will be put in place to protect those individuals, and provide the rationale for including this population in the research study. For information on additional protections, please see the 'Supplemental Guidance' section of the [CRC IRB webpage](#).

BU students and employees may be enrolled if ALL the following conditions are met:

- The student/employee is aware that participation in the study is completely voluntary and will not be used to sway benefits or employment status
- The student/employee has had ample time to read over the consent form
- The investigator taking informed consent must be someone other than the PI and must not be in a senior or supervisory role to the student/employee
- The investigator taking informed consent must be trained in taking consent

No student/employee can consent themselves to participate in this interventional study. Any BU employee, student, or staff *who is a direct member* of any of the research labs leading this study may participate in the study but will not be compensated. BU students who are not directly affiliated with any of the research labs leading this study may participate in the study and will be compensated for their time.

### Eligibility Criteria

#### Inclusion Criteria (Healthy):

- Age 18-80 years old
- No known, self-reported neuromotor disorder, gait pathology, or comorbidity that would interfere with participation (musculoskeletal, cardiovascular, neurological, skin, and vasculature conditions)

Inclusion Criteria (Stroke):

- Age 18-80 years old
- Diagnosis of a stroke
- Observable gait deficits (confirmed at secondary screening visit)
- Independent ambulation (with or without an assistive device) for at least 30 meters (confirmed at secondary screening visit)
- Full range of motion in ankle (confirmed at secondary screening visit)
- Ability to follow a 3-step command (confirmed at secondary screening visit)
- Resting heart rate between 40-100 bpm (confirmed at secondary screening visit)
- Resting blood pressure between 90/60 and 170/90 mmHg (confirmed at secondary screening visit)
- Provide HIPAA Authorization to allow communication with healthcare provider as needed during the study period
- Medical clearance by a physician

Additional Inclusion Criteria (Group 1: active rehabilitation):

- Currently undergoing active rehabilitation (independent of research procedures for this study) under the guidance of a therapist/physiatrist.

Additional Inclusion Criteria (Group 2: no active rehabilitation):

- Not currently receiving active rehabilitation (independent of research procedures for this study) under the guidance of a therapist/physiatrist.

Exclusion Criteria (Healthy):

*Note: Exclusion criteria are the specific criteria which would disqualify an individual from participating in the study, not simply the opposite of the inclusion criteria.*

- Diagnosed or self-reported neuromotor disorder or gait pathology
- Serious co-morbidities that may interfere with ability to participate in this research (musculoskeletal, cardiovascular, neurological, skin, and vasculature conditions)

Exclusion Criteria (Stroke):

*Note: Exclusion criteria are the specific criteria which would disqualify an individual from participating in the study, not simply the opposite of the inclusion criteria.*

- History of lower extremity joint replacement (i.e. hip, knee, ankle)
- Severe aphasia and/or speech/language disorder, limiting ability to express needs and comprehend instructions
- Shows signs of neglect or hemianopia
- Serious comorbidities that may interfere with ability to participate in the research (e.g. musculoskeletal, cardiovascular, pulmonary)
- Metal implants, pacemakers, and/or similar implantable devices that could be affected by the FES
- Pressure ulcers or skin wounds located near human-device interface sites
- More than 2 unexplained falls in the previous month

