**Phase 3: Clinical Training Studies** – This phase focuses on developing and studying novel therapeutic interventions that use the device. Participants who are suitable for moderate-to-high intensity activities (as determined by the research physical therapist) will be eligible to participate in this phase. Study visits will be used to assess potential long-lasting therapeutic benefits of training with the device. We will target keeping participants in this phase within 80% of their heart reserve, computed using their age-predicted maximum heart rate. Only Group 1 and Group 2 participants may participate in this research phase.

Enrolled participants who have had a stroke are eligible for all research phases, whereas participants who have not had a stroke are eligible for research phases 1 and 2. These research phases can be conceptualized as a categorization of the testing procedures being performed for the current development goals of the project. Due to the fluidity of device development and the need for reiteration, testing throughout this study may not follow a linear trajectory from Phase 1 to Phase 3. Rather, we will draw from the pool of enrolled participants to perform testing to inform the development of the reNeu neuroprosthesis, which may be development, testing, or training in nature. Enrolled participants may decline to participate in any of the phases, or they may participate in more than one phase. Participants who perform testing in one research phase will not be asked to repeat procedures in that same phase.

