### **Study Visit Procedures:**

Figure 1 provides an overview of the study flow. All eligible participants who have had a stroke will complete primary screening and secondary screening before being enrolled in the appropriate

group. Medical clearance and consent will also be obtained prior to testing. All eligible participants who have not had a stroke will complete primary screening before being enrolled in the Healthy group.

In-person visits will:

- Take place at one of the IRB-approved study locations, which include Boston University, Harvard University, or Spaulding Rehabilitation Hospital.
- Be conducted under the supervision of a trained investigator who will actively monitor the participant to ensure that physiological parameters stay within the established guidelines found on Table 1.
- All participants will follow exercise intensities determined based on an age-predicted heart rate (HR) maximum calculation:  $\text{max HR} = 208 - (0.7 \times \text{age})$ ; and a HR reserve calculation using Karvonen's formula:  $\text{HR reserve} = \text{max HR} - \text{resting HR}$ . Training intensities will be set at 60-80% of HR reserve. A training HR at 60% of HR reserve is calculated as:  $\text{resting HR} + 0.6 \times (208 - 0.7 \times \text{age} - \text{resting HR})$ . A training HR at 80% of HR reserve is calculated as:  $\text{resting HR} + 0.8 \times (208 - 0.7 \times \text{age} - \text{resting HR})$ . If a participant is taking beta blockers, HR parameters will be reduced by 10 bpm. These parameters are adapted from a clinical trial that implemented stepping practice in stroke at high intensities.
  - Participants will remain at or under 60% of HR reserve for Phase 1 study visits.
  - Participants will remain at or under 80% of HR reserve for Phase 2 study visits.
  - Participants will remain at or under 80% of HR reserve for Phase 3 study visits.
- Utilize safety belts and harnesses as necessary to minimize the risk for trips/falls.
- Provide seated or standing rest periods as needed or requested by the participant.
- Sessions that involve use of an exosuit will use either the exosuit developed by the Harvard Biodesign Lab (V2) or the commercial adaptation of the exosuit (ReWalk ReStore). These devices are functionally comparable.

[figure not shown]

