***Phase 1: Device Development (up to 3 visits per device iteration at any testing site)***

Device development visits will be no more than **5 hours each** in total duration. These visits will consist of no more than 60 minutes of cumulative walking, including no more than 15 minutes of continuous walking at one time. On average, participants will walk for less than 6 minutes continuously and will be provided with resting breaks between subsequent walking trials. Data may be collected while the participant is performing activities or while in a seated or supine position. The activities performed during each visit will vary depending on the design objective and the participant's functional abilities. However, most study visits will include electrode placement and tuning, inertial sensor and/or EMG donning, treadmill and/or overground walking with and without varying levels and durations of FES assistance. Rest breaks will be provided as needed, and physiological/stimulation parameters will be verified by a physical therapist to ensure the safety and comfort of participants. If the participant is unable or unwilling to complete a particular activity, that task is dropped from the visit plan, and the study team will assess whether it is safe and/or feasible to modify or continue with the rest of the visit.

Research in this development phase will facilitate the design of adaptive FES systems for post-stroke gait rehabilitation. Participants may be tested across multiple visits to facilitate evaluation of the reliability of the system and algorithms. System prototypes will be tested in the lab (e.g. at BU or HU), clinic (e.g. at SRH), or in the community (e.g. a neighborhood).

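### The exclusion of implants that stimulation could affect is listed for stroke participants only, although Healthy participants may also be stimulated

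*Protocol*

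**What the plan says.** **Who may enrol.** Protocol Section I plans for "up to 40 participants who have had a stroke and 40 participants who have not had a stroke", with a cap of 80 across all sites.

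**Stroke exclusions (Section I).** Two items concern the device: "Metal implants, pacemakers, and/or similar implantable devices that could be affected by the FES" and "Pressure ulcers or skin wounds located near human-device interface sites". The same list also carries its own general line on serious comorbidity.

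**Healthy exclusions (Section I).** There are two items: "Diagnosed or self-reported neuromotor disorder or gait pathology" and "Serious co-morbidities that may interfere with ability to participate in this research (musculoskeletal, cardiovascular, neurological, skin, and vasculature conditions". The Healthy inclusion criteria add that the person must know of no comorbidity, in the same five areas, that would get in the way of taking part. That line does not require the comorbidity to be serious.

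**Exposure (Section L).** Under Research Phases, "participants who have not had a stroke are eligible for research phases 1 and 2". In Phase 1, "most study visits will include electrode placement and tuning", followed by walking with and without stimulation. In Phase 2, testing visits begin with electrode placement and tuning.

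**Route of entry (Section L).** "All eligible participants who have not had a stroke will complete primary screening before being enrolled in the Healthy group". Primary screening may be done by telephone. The Medical Clearance paragraphs seek physician clearance for Groups 1 and 2, and exclude Healthy candidates who report a medical condition that could make participation risky.

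**The concern.** The implant exclusion is justified in its own words by what stimulation might do to the implant. That reason applies to anyone who wears the electrodes, with or without a stroke. If the Healthy list is applied item by item, a fit volunteer with implanted hardware can meet it, although the same hardware could disqualify a stroke participant.

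What is at stake is participant safety and the consistency of the eligibility rules. The group that lacks the device-specific item is also the group for which the protocol does not plan a secondary screening visit or, on most of its text, a physician's clearance.

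**Working it through.** No sample size, power or error rate is involved. The check sets the passages side by side.

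**1. Is the criterion about stroke or about the stimulator?** The stroke item covers only implants that stimulation could affect. The SAP's Study Participants section points the same way: it reports excluding people with metal implants beneath the stimulation sites.

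**2. Compare the lists.** Of the two device-related exclusions (implants; wounds near the device), the Stroke list names 2 of 2 and the Healthy list 0 of 2.

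**3. Does the general comorbidity line already cover implants?** The Stroke list has a general comorbidity line and still names implants separately. If the general line were meant to cover implants, the separate item would be redundant. The Healthy list has only the general wording.

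**4. Are Healthy participants stimulated?** They may enter Phases 1 and 2 but not Phase 3. The activity list for research visits in Section L, part (d), includes wearing electrodes while relaxed muscles are stimulated. Neither that list nor the Phase 1 and Phase 2 descriptions exempts the Healthy group.

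**5. What else protects the Healthy group?**

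| Safeguard | Where in the Protocol | Names implants? |
|---|---|---|
| Comorbidity wording, inclusion and exclusion | Section I | No |
| Primary screening questions on medical conditions and past use of electrical stimulation | Section L, part (a) | Not in the text; form not supplied |
| Exclusion on a self-reported risk condition | Section L, Medical Clearance | No |
| Eligibility re-check before each later visit | Section L, part (c) | No in the text, and it re-applies the same lists; form not supplied |
| Review of medical and physical history at each visit | Section L, part (d) | No |
| Skin inspection before electrodes are applied | Section L, Electrode Placement Procedures | No; covers skin only |

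The account of stimulation risks in Section M does not mention implants either.

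**6. Is there a physician check?** Study Visit Procedures, Medical Clearance and the risk-minimisation list in Section M all confine clearance to stroke participants. Section L, part (d), makes participants eligible for research visits once clearance has been obtained, and does not set the Healthy group apart. These passages do not agree.

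**7. Size.** 40 + 40 = 80, which matches the stated cap. The Healthy ceiling is 40/80 = 50% of target enrolment. The documents give no figure for how many volunteers have a relevant implant, so the number affected cannot be computed.

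**The case against.** The strongest reply is that the Healthy group is not unprotected. The self-report rule is mandatory, specific to that group, framed around risk and not limited to serious conditions. The Healthy inclusion line is also broader than the exclusion line. A volunteer who mentions a pacemaker would very plausibly be excluded under either rule. History is reviewed at every visit, eligibility is re-checked, and a physical therapist verifies the stimulation parameters. On this view the remaining risk is a failure to ask or to disclose, which is narrower than having no rule.

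Much of this stands. It makes the pacemaker case the less likely route to harm. It does not settle the case of other hardware: each of these checks depends on someone asking about implants, or on the volunteer regarding an implant as a medical condition or a comorbidity. A well person may not.

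Skin wounds are a second matter. A reader might infer that they are left open too, because that item also appears only in the Stroke list. The documents do not support this. Both Healthy criteria name skin conditions, and the electrode procedure requires inspected, intact skin for anyone who is stimulated.

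A third reply is that the Phase 2 mode descriptions speak of assisting the paretic limb, which a Healthy participant does not have. That wording fits stroke participants, but it is not an exemption, and the Phase 1 text and the activity list carry no such limit.

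**Conclusion.** The point holds for implants. An exclusion whose stated reason is the stimulator is missing from the criteria of one group that may be stimulated, and none of the general safeguards described in the text names implants.

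It rests on two assumptions. The first is that some Healthy visits in Phases 1 or 2 involve stimulation, which the text allows and nowhere rules out. The second concerns the primary and pre-visit screening forms, which were not supplied. They may ask about implants, but a question on a form would not by itself make an implant an exclusion.

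Three stronger readings go too far:

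- **Half of enrolment is at risk.** The 50% is the ceiling for the Healthy group. Those affected are the unknown few with a relevant implant who report no risk condition.
- **Healthy participants have no check after a telephone call.** Later re-screening and the history review at each visit contradict this.
- **Healthy participants certainly go without clearance.** That is the likelier reading, but the sentence in Section L, part (d), leaves it unsettled.

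The SAP analysis covers ten stroke participants and does not change. This is a moderate, cheaply corrected inconsistency with partial safeguards already in place.

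**What to change.** 1. Reconcile the two exclusion lists in Protocol Section I. Either the implant item covers every group that may be stimulated, or the protocol states why the Healthy group is exempt. The choice is for the investigators.
2. Check that the Healthy primary screening form and the Pre-Visit Screening Form ask about implants, and add the question only if it is missing.
3. Reconcile the clearance sentence in Section L, part (d), with Study Visit Procedures, Medical Clearance and the risk-minimisation list in Section M, so that it is clear whether Healthy participants need clearance.

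The cost is a minor amendment and possibly one or two screening questions. If the item is extended, a few volunteers may become ineligible.
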